#### *E. Summary and Rationale:*

Studies which identify validated surrogate markers at baseline or soon after starting treatment that can predict response to treatment have the potential to refine the standard of care for depression, as these predictor studies will reduce the amount of time that clinicians spend adjusting treatments to find the most optimal treatment option. Additionally, studies which compare predictive biomarkers between treatments, particularly between psychotherapy and pharmacotherapy, will further enable clinicians to choose an optimal treatment.

To our knowledge, QEEG has not been studied in the prediction of response to CBT, an important and widely used non-pharmacologic approach to treating depression. Establishing QEEG technology as a predictor of response to CBT could help to guide treatment selection for individual patients. It is probable that certain patient populations are more likely to respond to either psychotherapeutic or psychopharmacological interventions, while others may benefit from a combination of treatment modalities. The public health significance of a valid technology that provides an objective means of determining likelihood of response to treatment would be enormous. This study will provide preliminary information about the utility of QEEG as a predictor of response in psychotherapy and will furnish the knowledge base of QEEG changes related to clinical variables, providing pilot data for a study in a larger sample.

Additionally, very few studies have assessed changes in reward responsiveness as a function of treatment. It is possible that CBT and pharmacological interventions have different effects on reward responsiveness and anhedonia, and thus the use of this task will allow us to investigate the influence of different treatments on reward processing in this population. We expect that the results of this study will guide future research with the ultimate goal of identifying a behavioral indicator of underlying dysfunction in reward related brain regions. Finally, it is possible that the reward responsiveness will act as a predictor of response to both psychotherapy and pharmacological treatment.

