## **II. Specific Aims:**

Primary Aim 1: To determine whether QEEG technology can predict whether a patient with MDD will respond to CBT.

Hypothesis 1: Clinical response (defined as >50% change in HAMD-17 from beginning to endpoint) will correlate with changes in QEEG metrics (ATR, EEG Bispectrum, cordance estimates) from beginning to two weeks after starting treatment.

Primary Aim 2: To determine whether there are unique biological changes in patients undergoing CBT, as measured by the QEEG, that are different than those associated with antidepressants (SSRIs).

Hypothesis 2: QEEG parameters, different from those that predict response to pharmacotherapy, will be associated with response to CBT.

Secondary Aim 1: To determine whether there are correlations between QEEG patterns and changes in clinical functioning, assessed by clinical and self-rated instruments (SF-36, Symptom Questionnaire, Beck Depression Inventory), in both arms (CBT vs. escitalopram).

Secondary Aim 2: To determine whether there are any correlations between QEEG metrics and clinical variables (gender, age, comorbid anxiety, chronicity of depression).

Secondary Aim 3: To determine whether the behavioral processes associated with reward responsiveness in a depressed population change as a function of treatment.

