#### **IV. Subject Enrollment**

*A. Methods of enrollment/registration/randomization:*

Patients are usually screened by telephone to determine tentative eligibility for studies. The subjects then are invited to come to MGH for a full psychiatric diagnostic interview. Patients accepted into the study will be registered through the Depression Clinical and Research Program. Randomization numbers will be provided by the study Biostatistician and will be maintained by the research pharmacists at MGH Research Pharmacy, who will administer the open label escitalopram, 10-20 mg/day, to those subjects who have been randomized to receive medication. The randomization will be 1:1, i.e. half of the patients will be randomized to receive escitalopram (10-20 mg/day, flexible dose) and half will be randomized to receive twelve weekly 50-minute

Cognitive Behavioral Therapy sessions. Both treatment interventions have been strongly validated by the literature, and are considered standard of care for this population.

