The Signal Detection Task will be administered at baseline and at endpoint. In the specific Signal Detection Task we will use, called the Face Game (assessing reward sensitivity), we will present simple cartoon faces (diameter: 25 mm; eyes: 7 mm) in the center of the monitor and at the beginning of the trial. The face has no mouth. After a given delay, either a straight mouth of 11.5 mm (“short mouth”) or 13 mm (“long mouth”) will be presented for 100 ms. Subjects will be instructed to press an appropriate button to decide whether a long or short mouth had been presented. For the present study, the experiment will consist of 300 trials, divided into 3 blocks of 100. Long and short mouths will be presented equally often. A trial will begin with the presentation of an asterisk for 500 ms that will serve as fixation point and warning stimulus that a trial will start. After 500 ms, a mouth-less face will be presented and will stay on the screen until a response is made; after an inter-stimulus interval of 500 ms, one of the two mouths will be presented for 100 ms. Critically, not all correct responses will receive feedback (only positive feedback will be provided). For each block, 40 correct trials will be followed by a reward feedback (“Correct!! You won 5 cents”), presented for 1750 ms immediately after the correct response. For half of the subjects, correct identification of the little mouth will be associated with three times more positive feedback (30/40) than correct identification of the big mouth (10/40). For the other half of the subjects, the contingencies will be reversed. After feedback, an inter-trial interval (ITI) of 250 ms will follow. Subjects will be instructed that the aim of the study is to win as much money as possible, and that they will receive the amount of money won at the end of

experiment (actual money will be shown to the subjects for increasing the credibility of the experiment).

Scales:

Once the patient has agreed to participate in the study by signing the informed consent, the following instruments will be administered by a study assessor who is blind to treatment condition at screen, baseline, and visits 4, 8 and 12:

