## VI. Statistical Analysis

- a) *Statistical Plan:* The Mann-Whitney U test will be used to analyze differences in changes of QEEG between responders and non-responders to CBT. We will use logistic regression with the outcome being response/no response on the HAMD-17 and the predictors being other EEG measures. We will test the predictors in a stepwise manner given the limited power with a small N. A power calculation based on a previous QEEG study conducted in our clinic reveals that, to achieve power = 0.80, we would need 34 subjects per group. With N = 30 per group (60 subjects total), our power is 0.76. Power for the current study, with N = 15 per group, is 0.47. While this study is underpowered due to the small N, the goal of this study is to act as a pilot study which can help measure effect sizes, providing a foundation for future, larger projects.

For secondary aims, we will use Pearson r's for pairs of continuous measures, or point-biserial r for pairs of dichotomous and continuous measures.

Data from the Signal Detection Fact Task will be analyzed by [name] at Harvard University. Response bias will be the main variable of interest, whereas reaction time, hit rates, and discriminability values will provide control variables. Analyses of variance (ANOVAs) will be used to investigate variables across the three blocks. Discriminability and response biases will be computed using standard formulae (e.g. McCarthy and Davidson 1981).

- b) *Study Endpoints:* Endpoints will be defined as the final study visit at the end of the 12 weeks, or the termination/final visit for patients who choose to (or have to) end participation in the study prematurely.

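### The only model named for the reward task is an ANOVA across within-session blocks, so as written it does not test Secondary Aim 3, which is about change with treatment

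*Protocol*

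**What the plan says.** Secondary Aim 3 (Protocol, II. Specific Aims) is: "To determine whether the behavioral processes associated with reward responsiveness in a depressed population change as a function of treatment". The rationale (I.E) adds a comparison between treatments: "It is possible that CBT and pharmacological interventions have different effects on reward responsiveness and anhedonia". Allocation (IV) is stated as "The randomization will be 1:1", with 30 patients in all, so 15 per arm.

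Section V a) gives the schedule, "The Signal Detection Task will be administered at baseline and at endpoint", and the structure of each sitting: "the experiment will consist of 300 trials, divided into 3 blocks of 100".

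The statistical plan (VI a) has a short paragraph for this task. It says "Response bias will be the main variable of interest", lists reaction time, hit rates and discriminability as control variables, and then states the model: "Analyses of variance (ANOVAs) will be used to investigate variables across the three blocks". Just before that paragraph is a general sentence: "For secondary aims, we will use Pearson r's for pairs of continuous measures, or point-biserial r for pairs of dichotomous and continuous measures".

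The SAP describes t tests of QEEG change by responder status. It does not mention the reward task.

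**The concern.** The aim compares two occasions twelve weeks apart and, by the rationale, two treatments. The one factor named for the ANOVA is block, which divides a single sitting into thirds. An ANOVA on block shows whether response bias builds up over 300 trials. It does not show whether bias at endpoint differs from bias at baseline, or whether any such change differs between CBT and escitalopram.

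If the sentence is followed as it stands, the trial reports a block effect and Secondary Aim 3 goes without a test or an effect estimate. If analysts add terms on their own initiative, the choice of outcome, contrast and covariates is left until the data are in hand. The protocol describes the study as a pilot meant to supply effect sizes for larger work, and a block effect supplies none for treatment.

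**Working it through.** The plan gives no figure for the reward task. The power values in section VI (34 per group for 0.80; 0.76 at 30; 0.47 at 15) rest on an earlier QEEG study and do not bear on this aim. The check is therefore on what the named model can estimate.

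**1. What a block-only model estimates.** Write L for the block 3 minus block 1 difference in bias at baseline, and suppose treatment shifts endpoint bias by g.
- If the shift is the same in every block, g cancels from every block difference. The block effect averaged over visits is L, whatever g is.
- If treatment instead alters the within-session course by k, the block effect averaged over visits is (L + (L + k))/2 = L + k/2. Without a visit term, k cannot be separated from L.
- Running one block ANOVA per visit gives L and L + k with a p-value each, but no test of the difference between them.

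**2. Illustrative simulation.** Inputs: 15 per arm, 2 visits, 3 blocks, 4,000 runs, two-sided 0.05. The SDs are assumed, not taken from the documents: subject 0.7, visit 0.3, residual 0.6. Block-only means a repeated-measures ANOVA on block, averaged over visits. The other two columns use each patient's change in mean bias. Entries are the share of runs rejecting.

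| Truth | Block-only ANOVA | Baseline-to-endpoint change | Arm against change |
|---|---|---|---|
| No effects | 5% | 5% | 5% |
| Visit change 0.4 | 5% | 91% | 5% |
| Visit change 0.4, arm difference in change 0.6 | 5% | 86% | 69% |
| Within-session learning 0.4 only | 90% | 5% | 5% |

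The sizes 91%, 86% and 69% depend on the assumed SDs. The 5% for the block-only model in rows 2 and 3 does not: it follows from step 1.

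**3. Which contrast suits the aim.** Under the same assumed SDs:
- Change in mean bias over blocks: SD = sqrt(2 × (0.3² + 0.6²/3)) = sqrt(2 × 0.21) = 0.65.
- Change in the block 3 minus block 1 score: SD = sqrt(4 × 0.6²) = sqrt(1.44) = 1.20.

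With 15 per arm, 80% power at an assumed two-sided 0.05 needs d = 1.06 between arms. That is a raw arm difference of about 1.06 × 0.65 = 0.69 on mean bias, or 1.06 × 1.20 = 1.27 on the block-difference score. The latter also has expectation zero when treatment moves bias equally in all blocks. The visit-by-arm test should therefore be on response bias across blocks.

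**4. Precision available.** Between arms, power is 0.26, 0.56 and 0.75 for d = 0.5, 0.8 and 1.0. Within one arm (paired, n = 15), 80% power needs d = 0.78. These figures describe the sample size, not the harm done by the ANOVA sentence.

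**The case against.** **The correlation sentence may already cover the aim.** Aim 3 is a secondary aim. Arm is dichotomous and change in response bias is continuous, so a point-biserial r between them fits the general sentence, and it is equivalent to a two-sample t test of change by arm. This stands in part: a reader might infer that the plan holds no method that could serve Aim 3, and the documents do not support that. But the sentence names no variables, the reward task has its own paragraph with its own method, and this correlation would not test the overall baseline-to-endpoint change.

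**Silence is not exclusion.** The plan speaks of ANOVAs in the plural and does not say that block is the only factor. The aim and the two-visit schedule suggest that a comparison over time was intended. It is therefore too strong to infer that the plan rules out visit and arm terms. They are simply not named, and the simulation shows what a block-only model does, not that the analysts would stop there.

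**Retest effects are hypothetical.** A reader might infer that practice, or memory of which mouth was rewarded, will be reported as a treatment effect. No document gives a practice effect for this task or describes such an analysis. What stands is a risk: the same patients repeat the task and both arms are treated, so a visit effect could include retest effects. The protocol does not say whether the rewarded mouth is kept or switched at endpoint; that is missing detail only.

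**It is a secondary aim in a 30-patient pilot.** This limits the weight of the point. It does not remove it, because a pilot meant to yield effect sizes needs a model that estimates them.

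**Conclusion.** The point holds in limited form. The one model named for the reward task has a within-session factor and no visit, arm or change-score term, so as written it does not test Secondary Aim 3. The general correlation sentence could at most supply the arm comparison and is not linked to this task. The SAP does not fill the gap.

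The importance is moderate: one secondary aim lacks a matching named test, no figure in the documents changes, and the primary aims are unaffected. The conclusion rests on the wording of the aim, the schedule and the ANOVA sentence, not on the simulation's assumed SDs. The detectable differences of d = 1.06 between arms and d = 0.78 within an arm assume a two-sided 0.05 level, which the documents do not state, and both sessions from all 15 patients per arm.

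**What to change.** Replace the ANOVA sentence in section VI, and carry it into the SAP, with the following:

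- A mixed ANOVA on response bias with block (3 levels) and visit (baseline, endpoint) as within-patient factors and arm (CBT, escitalopram) as the between-patient factor.
- Visit-by-arm on response bias across blocks as the test of a treatment difference, and visit-by-arm-by-block as supportive.
- The visit effect, overall and within each arm, as an estimate with a confidence interval, with a note that it could include retest effects because there is no untreated group. Randomised arms share the retest exposure, which is why visit-by-arm is the cleaner contrast.
- Discriminability and reaction time kept as control variables alongside the hit rates already listed, and the rewarded stimulus (short or long mouth) as a factor where it was recorded.

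The cost is a little more analysis work and a few lines of text. The plan already collects the task data at both visits. The SAP's methods are written in the past tense, so if the task data have already been examined, the report should say when this model was specified.

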## VII. Risks and Discomforts

- a) *Procedures:* None performed

- b) *Cognitive Behavioral Therapy*: Risks and discomforts associated with receiving psychotherapy are generally considered modest, but can include a worsening of depressive and/or anxiety symptoms, and psychological discomfort associated with discussion of one's difficulties. Answering detailed questionnaires may create a mild degree of inconvenience for the subjects and coming in for CBT visits and blind assessor visits may be seen as time consuming and inconvenient. Patients will be given telephone numbers of the doctors involved in the study if they would like to talk about any discomforts. A general risk associated with treatment for depression includes the risk that depression may not respond to treatment. Subjects will be informed of these risks.
- c) *Drug*: Escitalopram has been used in over 1 million patients in the US and there is a large well-validated safety database for it. Most common side-effects include nausea, ejaculatory problems, diarrhea and insomnia. The risks posed to the subjects who participate in this study are real but small.
- d) *QEEG*: There may be some initial forehead redness after removal of the electrodes. This is temporary and considered normal. There are no known long-term effects of recording brain EEGs. All information associated with study participants that is shared with Aspect Medical Systems will be treated confidentially
- e) *Signal Detection Computer Task*: We do not foresee any risks or discomforts presented by this task.
- f) *Device*: Not applicable
- g) *Radiation*: None

### **VIII. Potential Benefits**

- a) *Potential benefit to individuals*: The study will potentially provide relief of depressive symptoms to participating patients. Subjects will also be compensated \$25 per QEEG (\$125 total for all 5 QEEGs), and will receive \$20 plus earnings per trial of signal detection (\$40 plus earnings in total). Subjects will also be offered up to \$25 travel reimbursement per visit.
- b) *Potential benefit to society*: This proposal investigates QEEG in the prediction of response to both CBT and escitalopram in patients with major depressive disorder. Establishing QEEG technology as a predictor of response to therapy and/or medications could help guide treatment selection for individual patients. Thus, the study will potentially further our understanding of the neurobiological differences which underly individual differences in responses to certain treatments. The study would be one of the first comparisons of baseline biomarkers between patients who respond to CBT versus those who respond to an SSRI, thus filling an important gap in our knowledge base of predictors of response to different treatments. Establishing QEEG as an accurate predictive tool would have an enormous impact on providing better care to patients suffering from major depressive disorder.

## IX. Monitoring and Quality Assurance

a) Independent Monitoring of Source Data: Documentation of the presence of any side-effect or adverse event will be completed at every visit and will be reported in accordance with AE reporting guidelines of the MGH IRB. Patients will be encouraged to contact the investigator or a member of her staff at any time between visits concerning adverse events or worsening of symptoms. An event that is deemed serious will be recorded in the patient's study binder and will be handled in an expeditious manner. A Safety Monitoring Committee, including Drs [name], [name], and [name], will review SAEs quarterly. Research assistants responsible for data collection and storage will be aware of and comply with all regulatory requirements related to adverse events. In the event that a patient becomes ill or is injured as a direct result of study participation, medical care will be made available. All adverse events will be followed to resolution and reported to the MGH IRB as serious in the event that they are unanticipated, possibly related to the study, and meet any one of the following criteria:

1. Fatal or life threatening
2. Requires prolonged inpatient hospitalization
3. Results in persistent or significant disability or incapacity
4. Congenital anomaly
5. Medical events that require intervention to prevent serious outcome
6. Cancer
7. Overdose
8. Results in substance dependency or abuse

Outcomes Monitoring: Treatment outcomes will be documented so that at study completion appropriate recommendations can be made for further treatment.

b) Safety Monitoring:

### Monitoring of Safety Data by the DSMB:

1. Unblinded Reporting – Safety information for this study will be reported to the DSMB in an unblinded manner. A statistical penalty will not be assessed for the ongoing unblinded review of safety by the DSMB. Unblinded data will not be released to the investigators unless necessary for safety reasons.

2. Range of Safety Reporting to the DSMB – It is considered necessary for the purpose of monitoring the safety of the study that the DSMB review not only adverse events (AEs) and serious adverse events (SAEs), but other data that may reflect differences in safety between treatment groups. This includes treatment retention rates, and reasons for drop-out, and laboratory values reflecting potential toxicity.

3. Serious Adverse Events – Expedited review will occur for all events meeting the FDA definition of Serious Adverse Events (SAEs) – i.e., any fatal event, immediately life-threatening event, permanently or substantially disabling event, event requiring or prolonging inpatient hospitalization, or any congenital anomaly. This also includes any event that a study investigator or the DSMB judges to impose a significant hazard, contraindication, side effect, or precaution.

For purposes of this study, all SAEs will be required to be reported to the DSMB, regardless of any judgment of their relatedness to the study drug. All relevant information will be reported to the DSMB for each SAE including information about the event and its outcome, dosing history of all study drugs, concomitant medications, the subject's medical history and current conditions, and all relevant laboratory data. Notification by e-mail, and FAX transmittal of all related study forms shall be made to the DSMB within 2 days of the occurrence of any SAE. Information will be reviewed and a determination made of whether there was any possible relevance to the study drug. Additional reporting to local IRBs will be done within 24 hours of the SAE.

4. Non-Serious Adverse Events – At periodic intervals (quarterly during the course of the study and then again at its completion), the DSMB will be provided with un-blinded summaries of the numbers and rates of adverse events by treatment group. These reports will include types of events, severity, and treatment phase. Data on individual non-serious adverse events is not expected to be needed for this review.

5. Other Safety-Related Reports – At three-month intervals throughout the course of the study, the DSMB will also receive unblinded summary reports of treatment retention and reasons for dropout, by treatment arm and study phase.

6. Study Stopping Rules – If at any time during the course of the study, the DSMB judges that risk to subjects outweighs the potential benefits, the DSMB shall have the discretion and responsibility to recommend that the study be terminated.

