## V. Study Procedures

### a) *Study visits and parameters to be measured:*

The study involves the enrollment of 30 outpatients with major depressive disorder.

Patients screened for the study and found to be eligible will return for their baseline visit after one week, at which eligible patients (n = 30) will be randomized to either CBT or to standard pharmacotherapy with an SSRI (escitalopram 10-20mg) for 12 weeks.

The CBT group will receive twelve weekly 50-minute individual sessions over the course of 12 weeks conducted by experienced therapists who are trained in manual based CBT. The medication group will receive open label treatment of escitalopram, 10-20 mg/day, flexible dose, for 12 weeks, and will be seen every two weeks by a study physician. In both arms, study assessors, who are blind to treatment condition, will assess patients monthly (week 0, 4, 8, and 12), and are responsible for the primary outcome measure (HAMD-17).

The QEEG will be administered 5 times during the study (week 0, 1, 2, 8 and endpoint) allowing us to assess whether there are any correlations between QEEG patterns and changes in clinical functioning. We will record EEG from a fronto-parieto-temporal derivation using a 4-channel EEG Monitor (Aspect Medical Systems) connected to the subject via disposable EEG electrodes. The adhesive material of the electrodes is similar to that found in ECG electrodes. All recordings will be analyzed off-line to generate QEEG metrics. Once such QEEG metric, the ATR, is a complex index derived from left-right asymmetry of combined theta+alpha (4-12Hz) power, relative theta power, and percent change from baseline in relative theta power, and ranges from 0 (low probability of response) to 100 (high probability of response). De-identified data will be shared with Aspect Medical Systems for offline calculation of EEG-based metrics.

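### The SAE causality determination in the DSMB section is worded only against the study drug, so for the CBT arm it never asks whether an event may be related to CBT

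*Protocol*

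**What the plan says.** The relevant text is in Protocol section IX, b) Safety Monitoring, under the heading on DSMB monitoring of safety data, item 3 (Serious Adverse Events). It has three parts.

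- Reporting: "all SAEs will be required to be reported to the DSMB, regardless of any judgment of their relatedness to the study drug".
- Information supplied for each SAE: all relevant information is to be sent, including the event and its outcome and "dosing history of all study drugs, concomitant medications, the subject's medical history and current conditions, and all relevant laboratory data".
- Causality: "Information will be reviewed and a determination made of whether there was any possible relevance to the study drug".

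The design is in sections IV and V. Section V states: "The study involves the enrollment of 30 outpatients with major depressive disorder". Section IV states: "The randomization will be 1:1, i.e. half of the patients will be randomized to receive escitalopram", and the other "half will be randomized to receive twelve weekly 50-minute" CBT sessions. Neither section describes any study drug for the CBT group.

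Section VII b) lists the risks of CBT, which "can include a worsening of depressive and/or anxiety symptoms", along with psychological discomfort from discussing one's difficulties.

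Section IX a) uses a broader test for reporting an event to the hospital IRB as serious. The event must be unanticipated, must be possibly related to the study as a whole (not to the drug), and must meet one of a list of seriousness criteria.

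**The concern.** Item 3 reads as if it were written for a trial in which every participant takes a study drug. Here half of them do not. If relatedness is judged only against the drug, the answer for a CBT patient is fixed before anyone looks at the event. The protocol itself accepts that CBT can do harm, and the harm it names, worsening depression or anxiety, could lead to a hospital admission that meets the item 3 definition of an SAE.

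What is at stake is the safety record. For a CBT-arm SAE, the causality entry would say something true about escitalopram and nothing about the treatment the patient received. Anyone who later reads those entries as relatedness to study treatment would be misled.

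**Working it through.** Apart from the size of the arm, this is a matter of reading the text. The documents give no SAE rate, and none is needed.

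**1. Number of patients affected.** Inputs: 30 patients (section V) and 1:1 allocation (section IV). CBT arm = 30 × 1/2 = 15. This reproduces the 15 per group stated in section VI a). The share is 15/30 = 50% of patients. This is a count of patients to whom the rule applies, not of events.

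**2. What the rule can return in each arm.**

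| | Escitalopram arm (15) | CBT arm (15) |
|---|---|---|
| Study drug received | Yes | None described |
| Item 3 question: possible relevance to the study drug | Yes or no | No only |
| Treatment-exposure item listed in item 3 | Dosing history | None listed |
| Question about relation to CBT or study procedures | Not asked | Not asked |

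An SAE in a patient never given the drug cannot be relevant to it. In the CBT arm the determination therefore carries no information.

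**3. Whether the listed information fills the gap.** The one treatment-exposure item named is "dosing history of all study drugs". Two other listed items are also thinner in the CBT arm. Section V schedules questions about changes in concomitant medication for the medication arm, and its sentence on psychotherapy patients mentions only adverse events. Section V also limits the blood count, chemistry, urinalysis and EKG to the medication arm. The list in item 3 is introduced as illustrative, so CBT attendance is not excluded, but nothing prompts anyone to supply it.

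**4. Whether another provision asks the missing question.**

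- Section IX a) uses the broader test of relation to the study, which can cover CBT. It governs IRB reporting and requires the event to be unanticipated. Worsening depression is a disclosed CBT risk, so it could be treated as anticipated and fail that test.
- Item 3 also requires reporting to local IRBs within 24 hours, with no relatedness condition. It adds no causality question about CBT.
- Item 4 (adverse event numbers and rates by treatment group), item 5 (retention and dropout reasons by arm) and item 6 (stopping) do not depend on relatedness. They neither carry the defect nor repair it.

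**5. A worked case.** Suppose a CBT patient is hospitalised for worsening depression. The event goes to the DSMB within 2 days with the arm known, because safety reporting is unblinded (item 1). The determination is then made against escitalopram, which the patient never took, and the answer is no. The written procedure has no step at which possible relation to CBT is recorded.

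**The case against.** The strongest reply is that this is a wording lapse with little practical consequence, because the rest of the safety system covers the CBT arm. Most of that stands:

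- All SAEs reach the DSMB promptly, unblinded and regardless of relatedness.
- Item 3 also takes in any event that an investigator or the DSMB judges a significant hazard or side effect, and this is not limited to the drug.
- Section V has the therapist assess adverse events at baseline and every two weeks to week 12.
- Section IX a) adds a committee that reviews SAEs quarterly.
- Nothing forbids the DSMB from considering CBT. Recording that an event is not relevant to escitalopram is a correct answer to a narrow question and does not clear CBT.

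Two stronger readings are tempting and should be put aside. A reader might infer that the DSMB's comparison of related serious events is biased in favour of CBT. The documents describe no tabulation or comparison of related SAEs by arm. What the DSMB compares by arm is adverse events and retention, neither filtered by relatedness. If someone did tabulate related SAEs by arm under this wording, the table would be uninterpretable, but that table is not planned.

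A reader might also infer that a CBT signal is hidden when the DSMB weighs risk against benefit. Item 6 rests on overall risk to subjects and mentions neither relatedness nor the drug, so the text does not support that.

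The reply does not remove the narrower point. A stated determination that can give only one answer for half the patients does not do its job, and no other DSMB provision puts the question it omits.

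**Conclusion.** The point holds as a defect in causality classification, of minor severity. For 15 of 30 patients the item 3 determination is fixed at not relevant, and the written procedure does not ask whether an SAE may be related to CBT, although the protocol names a CBT harm. Events are not lost, and no biased comparison, missed signal or changed decision is shown. The study's aims concern QEEG, clinical functioning and reward response, and none uses SAE relatedness.

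This rests on two readings. First, the determination sentence is passive and names no one. That the DSMB makes it is inferred from the heading and the preceding sentences. Second, the CBT arm receives no study drug. That is how the protocol describes it, but the SAP labels one of its analysis groups Drug+CBT, which does not match. The point follows the protocol's description.

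**What to change.** In section IX b), item 3, change both relatedness phrases (the one in the reporting sentence and the one in the determination sentence) to refer to *the assigned study treatment (escitalopram or CBT) or study procedures*. Both arms then face the same question, consistent with the broader wording in section IX a). It would also help to state who makes the determination.

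Add to the listed SAE information, for CBT patients, the dates and number of sessions attended.

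The cost is a change to the protocol text and the SAE form. Attendance at weekly sessions should already be known to the therapists. No visit, sample size or analysis changes. The one drawback is that causality is harder to judge for a psychotherapy than for a drug, so some CBT-arm events will be classed as possibly related.
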